9.3.2 Safety analysis

All safety parameters will be evaluated in an explorative or descriptive manner, providing proportions as applicable. The analyses will focus on the adverse events categorized and graded according to CTCAE v5.0. Adverse events will be summarised by treatment arm, body system and preferred term, intensity, and causal relationship to radiotherapy (in the experimental arm). Frequencies and percentages of any grade AE and grade 3-4 AE will be reported and eventually compared using Fishers' exact test.

Quality of life data will be analysed according to the corresponding scoring manuals; the details will be defined in the SAP.

The first safety analysis concerning wound healing disorders will be performed after n=100 patients, who received breast conserving surgery or an autologous flap (n=100 both together), as well as in patients, who received implant-based reconstruction after n=40 and n=100 patients. The Independent Safety Monitoring Board will perform a review and give recommendations for the study accordingly.

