2.1 Clinical rationale for preoperative radiotherapy in high-risk breast cancer

The NeoRad trial tests whether preoperative radiotherapy results in an improved DFS and less radiation induced late effects compared to postoperative radiotherapy in higher risk breast cancer after NACT. The aim of postoperative radiotherapy is to eliminate residual locoregional microscopic disease in non-resected tissues. The overall treatment time for this residual microscopic disease from the first cycle of NACT to completion of radiotherapy is about 3 to 6 weeks shorter, if preoperative radiotherapy is administered. This should result in an improved locoregional control, which is of special interest in view of the higher locoregional recurrence rates that have been reported after NACT compared to adjuvant chemotherapy [1]. Furthermore, residual disease potentially resistant to NACT has less time for metastatic spread. The advantage of preoperative radiotherapy has already been shown in randomized trials in other tumor entities like in rectal cancer and soft tissue sarcoma. In rectal cancer, neoadjuvant chemoradiation resulted in significantly better local control and functional outcome compared to postoperative chemoradiation [22]. Preoperative radiotherapy of 50 Gy in 25 fractions in soft tissue sarcoma has been shown to be equivalent in terms of local tumor control to a 32% higher dose (66 Gy in 33 fractions) postoperative radiotherapy. Late

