3.2 Secondary objectives

Assessment and comparison between randomized arms of

- 1) time to local recurrence [in affected breast] (LR) as a first site of recurrence: recurrence in affected breast counts as an event; regional recurrence, distant recurrence, contralateral breast cancer, invasive non-breast cancer, death due to any cause are considered competing risks.
- 2) time to regional recurrence (RR) as a first site of recurrence: recurrence in the regional lymph nodes counts as an event, local recurrence, distant recurrence, contralateral breast cancer, invasive non-breast cancer, death due to any cause are considered competing risks.
- 3) distant disease-free survival (DDFS): distant recurrence, invasive non-breast cancer and death due to any cause are considered as events.
- overall survival (OS): death due to any cause is considered as an event.
- 5) breast cancer specific survival (BCSS): death due to breast cancer is considered as an event; in case of unknown death cause all effort will be made to determine the cause; if at the time of analysis there are still any deaths due to the unknown reason, they will be counted as tumor-related (worst case principle).

Time for all time-to-event endpoints will be computed starting from randomization after end of NACT.

- 6) pathological complete remission (pCR, defined as ypT0/is ypN0) rates.
- 7) cosmetic results (5 Point Scoring System, key secondary objective and subjective
- 8) breast retraction assessment=BRA)
- 9) quality of life (EORTC C30 and EORTC QLQ-BR23)
- 10) rate of arm lymph edema >°I of the irradiated side
- 11) plexopathy >°I of brachial plexus of the irradiated side

12) acute (up to 3 months after the end of radiotherapy) and late (after 3 months) toxicity (CTC 5.0, LENT-SOMA)

Definitions of outcome measures (clinical Trials.gov):

1. local recurrence rate [in affected breast] (LR) [Time Frame: 6 to 10 years]
Rate of cancer that has recurred at the same location as the primary cancer. This is a way to measure how well the new treatment is working.
2. locoregional recurrence rate (LRR) [Time Frame: 6 to 10 years]
Rate of new cancer at any locations (regional lymph nodes, chest wall/mastectomy site) on side which was previously affected by the primary cancer.
This is a way to measure how well the new treatment is working.
3. disease metastases free survival (DMFS) [Time Frame: 6 to 10 years]

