4.4 Standard of care arm

Patients randomized to the standard of care arm will receive surgery according to the national S3 and AGO-guidelines including targeted axillary dissection (TAD), sentinel lymph node biopsy (SLNB) +/- axilla dissection (AD).

3-6 weeks later, when wound healing is complete, the adjuvant radiotherapy to the whole breast/chestwall will be administered.

According to the S3/AGO guidelines postoperative radiotherapy of the breast/chest wall +/- regional lymph nodes (5x 2.7 Gy per week to 40.5 Gy) is recommended. If indicated according S3/AGO guidelines, a boost radiotherapy (optional intraoperative radiotherapy with electrons = IOERT) should be administered either as simultaneous integrated Boost or as sequential boost (see below).

After breast conserving surgery:

Whole breast radiotherapy with 5x2.7 Gy/week → 40.5 Gy in 3 weeks
+/- boost either as integrated boost (5x 3.2 Gy, total dose 48 Gy) or as sequential boost (3x 3.5 Gy to 10.5 Gy, total dose 51 Gy) or intraoperative boost with IOERT (electrons 1x10 Gy)
+/- + lymph node irradiation (5x2.7 Gy/week → 40.5 Gy in 3 weeks)

After mastectomy:

- chest wall irradiation: 5x2.7 Gy/week → 40.5 Gy in 3 weeks
+/- lymph node irradiation (5x2.7 Gy/week → 40.5 Gy in 3 weeks)

The standard of care arm presented here is a brief summary, which does not claim to be exhaustive. For a detailed summary of the radiotherapeutic treatment in this study, refer to Chapter 6

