Every adverse event (AE) after radiotherapy will be coded, categorized and graded in regards of its severity according to v5.0. If an event cannot be categorized it will be captured in a written form and grade as follows:

Grade 1 - low

Event is noticeable but tolerable

Grade 2 - moderate

Event limits everyday life activities

Grade 3 - severe

Event prohibits everyday life activities completely

Grade 4 – life-threatening

Grade 5 - deadly

Event leads to patient's death

Every adverse event has to be evaluated in terms of causalities:

Every adverse event has to be documented regardless of the examining doctor's opinion whether there is a causality to radiotherapy or not.

Adverse events are first recorded before the start of local therapy (after neoadjuvant chemotherapy), then during local therapy and as part of the follow-up examinations .

The following common toxicities are documented as AE of Special Interest as a Grade 3 toxicity or worse: skin reaction, pain and feeling of pressure. Complaints that appear during local examination are also documented as AE: edema of the breast, inflammation, haematoma, seroma and wound healing difficulties. Documentation includes the type of event: beginning, distinctness/ severity.

Signs of illness, symptoms and changes in laboratory values that are causally connected should be summarised to one single disease.

Documentation should be based on the given examination sheets (CRFs). AEs are identified by the doctor and coded by the GBG.

All adverse events that have a connection to the study therapy need to be observed until they disappear or stabilise.

Additional examinations that are deemed necessary by the examining doctor should be documented and marked as such in the CRFs.

[°]III-V Adverse events should be documented within 2 weeks after discovery into the database.

The head of study in Duesseldorf will review the database periodically (minimum 4-week-interval).

A serious adverse event (SAE) in the context of the NeoRad trial refers to any unexpected or significant medical occurrence or outcome that results in one or more of the following:

- 1) Death of a participant

- 2) Life-threatening condition of a participant
- 3) Hospitalization or prolongation of existing hospitalization of a participant (exception: re-resection due to R1-status)
- 4) Disability or permanent damage to a participant

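### Section 9.3.2 breaks adverse events down by relationship to radiotherapy in the experimental arm only, although both arms are irradiated, so events judged related have no comparator

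*Protocol*

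**What the plan says.** Section 9.3.2 sets out the adverse event tables. The general rule covers both arms: "Adverse events will be summarised by treatment arm, body system and preferred term, intensity". The last item in the same list is "causal relationship to radiotherapy (in the experimental arm"), and the bracket limits that item to one arm without giving a reason. The comparison that follows does not depend on attribution: "Frequencies and percentages of any grade AE and grade 3-4 AE will be reported and eventually compared using Fishers' exact test".

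Elsewhere the protocol treats radiotherapy as common to both arms. In the standard arm (section 4.4), once the wound has healed, "the adjuvant radiotherapy to the whole breast/chestwall will be administered". Section 2.1 says that the same hypofractionated schedule, 40.5 Gy in 15 fractions, is used in both arms. On data collection, section 6.8 states: "Every adverse event has to be evaluated in terms of causalities". It names no arm.

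**The concern.** The trial varies the timing of radiotherapy, not whether it is given. Section 2.1 says it tests whether preoperative radiotherapy leads to "less radiation induced late effects compared to postoperative radiotherapy". A breakdown by relationship to radiotherapy bears on that question only if it is shown for both sequences. Shown for one arm, it yields a count of radiotherapy-related events for the preoperative sequence and a blank for the postoperative one. A reader of the safety report could take the blank as zero, or the count as an excess. The asymmetry works against the arm that the protocol expects to be gentler.

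Attribution also has some use here. Counts regardless of cause mix radiation effects with those of surgery and systemic therapy, and concurrent systemic therapy differs by arm: the table in section 6.3 permits capecitabine and T-DM1 together with radiotherapy in the standard arm but not in the experimental arm.

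**Working it through.** No arithmetic in the plan is at issue, so the check sets the relevant sections side by side.

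1. **Is the control arm irradiated?** Yes. Section 4.4 prescribes adjuvant radiotherapy, and section 6.4.7 gives the doses without distinguishing arms. Limiting relatedness to one arm therefore cannot be justified by a lack of exposure in the other.

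2. **Is causality collected in both arms?** Section 6.8 asks for it for every event and sets no limit by arm. It also asks that every event be recorded whether or not the examining doctor thinks radiotherapy caused it. On the protocol text, the standard-arm judgements would exist but go unreported.

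3. **What does the bracket remove?** In the list in section 9.3.2 it attaches only to the last item. Arm, body system, preferred term and intensity remain two-arm tabulations. The loss is the standard-arm half of the relatedness breakdown. Section 9.4 plans 913 patients per arm; that is the number randomised, and the number irradiated in the standard arm will be somewhat smaller.

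4. **Which toxicity comparisons remain?** Section 9.3.2 keeps any-grade and grade 3-4 events, with Fisher's exact test. Section 3.2 lists, for comparison between randomised arms, lymphoedema, brachial plexopathy and "acute (up to 3 months after the end of radiotherapy) and late (after 3 months) toxicity". Section 8.3 schedules acute toxicity visits in both arms and LENT-SOMA scoring at later follow-up. None of these needs an attribution column.

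5. **Would deleting the bracket be enough?** Not quite. Section 9.2.2 admits patients with breast surgery or at least one fraction, groups them by treatment received, and places patients who had surgery but no radiotherapy in the postoperative group. Section 4.6 adds that a small group (cT1/T2 cN0 treated by mastectomy) would usually have no indication for postoperative radiotherapy. By these rules the preoperative safety group consists of irradiated patients, while the control group can be mixed. If a fraction f of the control safety group was never irradiated, and no such patient has an event judged related to radiotherapy, then:

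   related-event rate over the whole control group = (1 − f) × rate among irradiated controls.

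   The control rate would be understated by the relative amount f. The protocol gives no value for f, so the size cannot be stated, but the direction is clear: the preoperative arm would look worse. Using irradiated patients as the denominator removes this.

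**The case against.** The strongest reply is that the affected table carries little weight. Section 9.3.2 calls all safety analyses explorative or descriptive. Attribution is made by investigators who know the arm, since the trial is open, so comparisons regardless of causality are the more reliable ones, and those are already planned for both arms. Section 9.6 leaves further analysis detail to the statistical analysis plan, and table layout usually belongs there.

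Most of this stands, and it sets the severity. It does not remove the point, because the bracket is a rule written into the protocol rather than a detail left open.

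Three stronger readings may tempt a reader, and the protocol supports none of them:

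- **That the trial cannot compare radiation toxicity between arms.** It can, through the all-cause, lymphoedema, plexopathy, and acute and late toxicity comparisons in sections 3.2, 8.3 and 9.3.2.
- **That the plan overlooks control-arm radiotherapy.** It does not. Section 9.2.2 names the post-surgery radiotherapy group, and section 8.3 asks for weekly toxicity assessment during radiotherapy without restricting it to one arm.
- **That the between-arm difference in related events can never be computed.** Section 6.8 calls for the judgements in both arms, so the difference should be recoverable from the collected data. What is missing is the planned display.

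**Conclusion.** The point holds in a limited form. Section 9.3.2 restricts the breakdown by relationship to radiotherapy to one of two irradiated arms, without a stated reason and out of step with section 6.8. Events judged related to preoperative radiotherapy would be presented with no postoperative comparator. The consequence is one lopsided descriptive table. The primary analysis, sample size, power and the other planned toxicity comparisons are untouched. Severity is minor.

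The conclusion assumes that the bracket is meant literally and that the case report form follows section 6.8 in asking for causality in the standard arm. The form is not among the documents. If sites or the form instead followed section 9.3.2, standard-arm attribution could be lost and the table could not be rebuilt later.

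**What to change.** - In section 9.3.2, delete the bracketed restriction to the experimental arm.
- Tabulate events judged related to radiotherapy by grade in both arms, among patients who received at least one fraction, and state how many patients in the control safety group were not irradiated.
- Keep the tables regardless of causality as the main safety comparison, and label the related-event table as supportive because attribution is unblinded.
- Confirm that the case report form records causality in the standard arm.

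The cost is a one-line text change and one more column in a table. No new data are needed if section 6.8 is being followed.

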			with (LDI) or without (ALD) implant			the rate of complications increased	(1.8%) secondary complications >1 month: n= 48 (43.2%) after the first month of post-operative surgery, shoulder adhesive capsulitis: n= 26 (23.4%), neurogenic pain: n=12 (9%), dorsal adherence pain: n=3 (2.7%), capsular contracture: n=3 (2.7%), fat necrosis: n=2 (1.8%), displacement of prothesis: n=1 (0.9%), scar disunity: n=1 (0.9%); major secondary complication: limitation of up to 45° of scapulo-humeral joint abduction n=26 (23.4%), neurological pain n=10 (9%); minor secondary complications: implant hernias, capsular contracture, painful dorsal scar adherence, nine surgical procedures had to be performed in order to treat primary or secondary complications, n =35 corrective reconstruction procedures	
Riet et al. [80], 2017, European Journal of Cancer	n=202 PreopRT, n=15 excluded, n=187 analysed	non-inflammatory and non-metastasized BC T2-T4 or N2 tumors n = 166 centrally reviewed tumor biopsy specimens: 22% triple-negative (TN) phenotype, 17% HER2 3+ or amplified and 61% ER+	RT with Cobalt-60 unit, slightly hypofractionated RT to whole breast, ipsilateral supraclavicular fossa and axilla ± internal mammary chain (45-55 Gy/18 fractions of 2.5 Gy/34 days) followed by modified radical mastectomy with axillary dissection	mastectomy	no preoperative chemotherapy, postoperative chemotherapy (CMF or anthracycline-based regimens) prescribed according to institutional guidelines n= 58 (31%)	modified radical mastectomy (MRM) with axillary dissection (AD) at least 4 weeks after the completion of radiotherapy, whatever tumor response	postoperative complication rate (grade>2) 19% with 4.3 % of localized skin necrosis; 30-day postoperative complication rate 19% (n=36); Grade ≥ 2 dehiscence of suture n= 7 (4%), Grade ≥ 3 skin necrosis n=8 (4%), n=9 patients (5%) second surgical procedure for grade 3 infection or haematoma, n=10 (5%) grade ≥ 2 lymphocele during early postoperative period, n=1 (0.5%) myocardial infarction, n=1 (0.5%) death 3 days after surgery due to a pulmonary embolism	NR

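### The severe adverse event rate in Section 9.3.2 stops at grade 4, so a patient whose only severe event is fatal counts as having none

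*Protocol*

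**What the plan says.** Section 9.3.2 names two AE rates: "Frequencies and percentages of any grade AE and grade 3-4 AE will be reported", with a possible comparison by Fisher's exact test. The same section sets the status of the analysis: "All safety parameters will be evaluated in an explorative or descriptive manner, providing proportions as applicable". It also plans a summary of AEs by arm, body system, preferred term, intensity and, in the experimental arm, causal relationship to radiotherapy.

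Section 6.8 sets how AEs are graded and captured:

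- Every AE is to be documented and graded by version 5.0 of the toxicity criteria. The fallback scale for events that cannot be categorised ends with "Grade 5 - deadly".
- On timing of data entry, grade "III-V Adverse events should be documented within 2 weeks after discovery into the database".
- Skin reaction, pain and feeling of pressure are "documented as AE of Special Interest as a Grade 3 toxicity or worse".
- Death is the first SAE criterion. SAEs are reported from the start of radiotherapy until 3 months after it.

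Table 1 in Section 3.1 lists treatment-related death as a separate event category of disease-free survival (DFS).

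**The concern.** A rate labelled as severe toxicity is normally read as covering the worst outcomes. This one excludes the worst of all. A patient who dies of a postoperative or radiation complication, with no other event above grade 2, sits with the mild events in the any-grade rate and counts as a non-event in the severe rate.

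The trial moves surgery into a recently irradiated field, and Section 4.6 accepts that more postoperative complications cannot be ruled out. Under Sections 3.1 and 9.3.1, if only non-inferiority is shown, the case for adoption rests on cosmetic results. A clean account of severe toxicity by arm would then carry weight. With the present definition, an arm with more fatal events could show an equal or lower severe rate.

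Such events are rare but not unknown in the series that the protocol cites. Table 5 records one "death 3 days after surgery due to a pulmonary embolism" (0.5%) and, in another series, one grade 5 pneumonitis (3%).

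**Working it through.** **The definitions side by side.** No stated sample size, power or significance level depends on this category, so there is no figure of the plan to reproduce.

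| Place | Grades covered | Grade 5 included? |
|---|---|---|
| 9.3.2, first rate | any | yes, with all milder grades |
| 9.3.2, severe rate | 3-4 | no |
| 9.3.2, summary by intensity | each grade | yes, descriptively |
| 6.8, two-week entry rule | III-V | yes |
| 6.8, events of special interest | 3 or worse | yes |

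Only the severe rate in 9.3.2 stops at grade 4, and no other section adds grade 5 to it.

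**Who is miscounted.** The protocol does not say whether a patient is classed by worst grade or by any event in the range. If any grade 3-4 event qualifies, only patients with a fatal event and no other grade 3-4 event are missed. If worst grade is used, every patient with a fatal event is missed.

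**How many.** Inputs: 913 patients per arm (Section 9.4) and an assumed fatal AE rate of 0.1% to 0.5%. The documents give no expected rate.

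- 913 × 0.001 = 0.9 patients
- 913 × 0.005 = 4.6 patients

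That is about 1 to 5 per arm, an upper bound at those rates because it supposes that none of these patients had another grade 3-4 event.

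**Effect on the comparison.** All counts below are assumed, for illustration only, with 913 per arm and experimental arm first. Rates are count / 913, and p-values are from two-sided Fisher's exact tests. Fatal cases are taken to have no other grade 3-4 event. The fatal counts reach well above the 1 to 5 per arm just derived, to stress the definition.

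| Grade 3-4 count | Fatal count | Grade 3-4 rate (p) | Grade 3-5 rate (p) | Fatal alone, p |
|---|---|---|---|---|
| 91 vs 91 | 5 vs 1 | 9.97% vs 9.97% (1.00) | 10.51% vs 10.08% (0.82) | 0.22 |
| 91 vs 91 | 9 vs 0 | 9.97% vs 9.97% (1.00) | 10.95% vs 9.97% (0.54) | 0.004 |
| 85 vs 91 | 9 vs 0 | 9.31% vs 9.97% (0.69) | 10.30% vs 9.97% (0.88) | 0.004 |
| 91 vs 91 | 14 vs 2 | 9.97% vs 9.97% (1.00) | 11.50% vs 10.19% (0.41) | 0.004 |

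For the second row: 91 / 913 = 9.97%, (91 + 9) / 913 = 10.95%, and 9 / 913 = 0.99% against 0%.

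Two things follow. First, the grade 3-4 rate can be equal between arms, or even lower in the arm with more deaths (third row). Second, adding grade 5 moves an arm's rate by at most 14 / 913 = 1.5 percentage points, and the pooled test stays far from any signal. Only a separate grade 5 count shows the imbalance.

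**The case against.** The strongest reply is that this is a row label in an exploratory table. No alpha, stopping rule or sample size hangs on it, and the comparison itself is only tentatively planned. The summary by intensity in the same section should already show grade 5 events by arm. Fatal events are also captured as SAEs and as DFS and overall survival events, and DFS has its own category for treatment-related death. Table layouts are commonly left to the statistical analysis plan.

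Most of this stands, and it rules out three stronger readings that a reader might infer.

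- *That deaths go unreported, or appear only in the any-grade rate.* The intensity summary and the other routes contradict this.
- *That survival endpoints never identify a death as due to treatment.* Table 1 in Section 3.1 does so by category, although Section 9.3.1 plans no comparison of that category.
- *That Section 6.8 makes grade 3 the threshold for reporting.* It requires every AE to be documented. Grade 3 or worse applies to three named toxicities, and III-V sets a data-entry deadline.

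The cited fatal cases are also weak guides to a rate. The pulmonary embolism followed mastectomy in a Cobalt-60 series without preoperative chemotherapy, and surgery takes place in both arms here. The pneumonitis followed radiation given concurrently with docetaxel, whereas here radiotherapy follows chemotherapy.

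Two parts of the reply do not hold. The cut-off is not left open: the protocol states it, and an analysis plan that followed it would carry it forward. Nor are SAE reports an even substitute. Their window opens with radiotherapy, which in the standard arm starts 3 to 6 (up to 8) weeks after surgery (Section 6.4.2). A postoperative death before radiotherapy in that arm falls outside the window, while surgery in the experimental arm, preferably 3 to 6 weeks after radiotherapy, falls inside it.

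**Conclusion.** The point holds in a limited form and is minor. As written, the severe rate in Section 9.3.2 gives a wrong count for any patient whose only severe event is fatal, and it conflicts with the groupings in Section 6.8. No stated number in the protocol is wrong, and fatal events are not lost from the trial's reporting.

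The likely size is at most about 1 to 5 patients per arm. This rests on an assumed fatal rate of 0.1% to 0.5% and on 913 patients per arm; the safety set, grouped by treatment received, may differ somewhat. The documents do not support a claim that the trial would miss a mortality difference. They support only the narrower statement that the one severe-toxicity rate named for comparison would not show it.

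**What to change.** In Section 9.3.2, change the severe category from grade 3-4 to grade 3 or higher (3-5), and add that the number of grade 5 events will be stated by arm. The second part is the more informative one, as the illustration shows, and it makes explicit what the summary by intensity already implies.

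The cost is a few words. No new data are needed, since Section 6.8 already captures grade 5, and the sample size, significance level and all other figures stay as they are.
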